 12.2 CONFLICT OF INTEREST **ERROR! BOOKMARK NOT DEFINED.**

 12.3 SUBJECT STIPENDS OR PAYMENTS 25

13 PUBLICATION PLAN 25

14 REFERENCES 26

15 ATTACHMENTS 27

List of Abbreviations**LIST OF ABBREVIATIONS**

AE	Adverse Event/Adverse Experience
BSA	Body Surface Area
CAILS	Clinical Assessment Scale of Severity for Index Lesion Signs & Symptoms
CFR	Code of Federal Regulations
CRF	Case Report Form
CXCR3	Chemokine Receptor-3
CXCL9	Chemokines Ligands 9
DEGs	Differentially Expressed Genes
DSMB	Data and Safety Monitoring Board
FDA	Food and Drug Administration
GCP	Good Clinical Practice
GVHD	Graft Versus Host Disease
HIPAA	Health Insurance Portability and Accountability Act
IB	Investigator's Brochure
IL-1	Interleukin-1
IND	Investigational New Drug Application
IFN α	Interferon Alpha
IFN γ	Interferon Gamma
IRB	Institutional Review Board
JAK	Janus Kinase
LP	Lichen Planus
LTR	Lichenoid Tissue Reaction
MDC	Myeloid Dendritic Cells
NRS	Numerical Rating Scale
PDC	Plasmacytoid Dendritic Cells
PGA	Physician Global Assessment
PHI	Protected Health Information
PI	Principal Investigator
SAE	Serious Adverse Event/Serious Adverse Experience
SOP	Standard Operating Procedure

Study Summary

Title	INCB018424 PHOSPHATE CREAM in the Treatment of Cutaneous Lichen Planus
Running Title	INCB018424 PHOSPHATE CREAM in LP
Protocol Number	17-005406
Phase	Phase II
Methodology	Open-Label, Single Arm
Overall Study Duration	13 to 16 weeks
Subject Participation Duration	12 weeks
Single or Multi-Site	Single Site
Objectives	To evaluate the safety and efficacy of INCB018424 PHOSPHATE CREAM in cutaneous LP as assessed by the change in Physician Global Assessment (PGA), Body Surface Area (BSA), Index Treatment and Control Lesion by Modified Clinical Assessment Scale of Severity for Index Lesion Signs and Symptoms (Modified CAISL) score, Pruritus Numerical Rating Scale (NRS), and Skindex-16. To predict responses through the identification of unique biomarkers of LP at week 0 and utilizing RNA sequencing on responsive and non-responsive tissue at week 4.
Number of Subjects	12
Diagnosis and Main Inclusion Criteria	Non-pregnant adults with cutaneous LP involving less than 20% of the body surface area (BSA)
Study Product, Dose, Route, Regimen	INCB018424 PHOSPHATE CREAM 1.5%, topical application, twice daily on lesions of cutaneous LP.
Duration of Administration	Drug will be administered from Day 0 through Week 8.

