To determine the efficacy of INCB018424 PHOSPHATE CREAM and the duration of response after discontinuation as measured by the change in Pruritus NRS, (week 0 to week 4, week 0 to week 8, weeks 4 to 8, weeks 8 to 12), Change in Skindex-16 (week 0 to week 4, weeks 4 to 8, weeks 8 to 12), Change in Physician Global Assessment (PGA) (week 0 to week 4, week 0 to week 8, weeks 4 to 8, weeks 8 to 12), Change in BSA (week 0 to week 4, week 0 to week 8, weeks 4 to 8, weeks 8 to 12), Change in Modified CAILS (week 0 to week 8, weeks 4 to 8, weeks 8 to 12).

Exploratory Objectives:

To predict responses and examine the pharmacodynamics of treatment through the identification of unique biomarkers and transcriptomic changes of LP at week 0 and utilizing RNA sequencing on responsive and non-responsive tissue at week 4 To correlate these biomarkers with measures of global response: Modified CAILS, PGA, BSA, and lesion count.

4 Study Design

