Individuals will then initiate treatment on all lesions of LP BID and will be evaluated weekly and assessed by PGA, BSA, lesion count; Modified CAILS, Pruritus NRS, and Skindex-16 between weeks 0-4 (see Appendix). Week 4 will be the primary endpoint; however therapy will be continued for an additional 4 weeks. Therapy will be stopped and the individuals will be evaluated at week 8 and assessed by PGA, BSA, lesion count, Modified CAILS, Pruritus NRS, and Skindex-16. Laboratory and safety monitoring will occur at weeks 1, 2, 3, 4, and 8, and 12. 3D Photographs will be taken at weeks 0, 1, 2, 3, 4, 8, and 12. Individual lesions will be circled at that time and the exact volume of each lesion will be measured. Up close photos will be taken of the disease and normal tissues attained at weeks 0 & 4.

Tissue will be collected for RNA sequencing at week 0 and 4. Blood collection will include the isolation at week 0, 2, and week 4, 5mL vials of blood which will be separated and the serum and cell pellet will be stored for future analysis. Five skin biopsies will be taken during the study. At week 0, up to two 3mm tissue biopsies will be taken from lesional skin and one biopsy will be taken from normal appearing skin. The initial biopsy of lesional tissue and control will be

annotated. At week 4, up to two 3mm biopsies will be taken from lesional responsive tissue and lesional refractory tissue. Responsive and non-responsive lesions will be determined by the change in Modified CAILS between week 0 and 4. Responsive will require a 50% reduction in Modified CAILS and non-responsive can have progression, no change, or up to a 50% reduction in Modified CAILS. The lesions will be chosen using full body photographs taken at week 0. Up to 60 samples will be snap frozen and stored in the tissue biobank. Once completed, RNA sequencing will be performed on the 60 tissue samples and analysis will be performed. Paired analysis of treatment responsive and refractory lesions will be made as well as treated and untreated lesions.

Nucleic Acid Extractions: RNA will be extracted from a total of 50 um of fresh tissue using the Qiagen FFPE RNeasy Micro extraction Kit according to manufacturer's recommendation.

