8.1 Sample Size Determination

Data analysis: Assuming a medium effect size (0.3) and a target power of 80%, a two-armed study would need about 108 subjects and a single arm about 88 subjects. Due to the costs associated with a study, we propose a single armed study of 12 subjects with corollary science including RNA sequencing. This will reduce costs and provide biomarkers predictive of response. Effect sizes will be estimated for the appropriate statistical tests that will be used for group comparisons in future studies. This will enable more accurate power and sample size estimates moving forward.

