8.2 Statistical Methods

Descriptive Statistics

Sample Size Computation and Power Analysis:

The sample size for this pilot study is set at 12 subjects for logistical and financial reasons. This is similar in size to other exploratory studies and will provide adequate data for estimation purposes for planning future studies. With 12 subjects, the study is intended to be for estimation purposes only.

Statistical Analysis Plan:

Data Analysis - The statistical analysis will provide descriptive summary statistics for categorical and continuous outcomes. Categorical variables will be described by their count and proportion of occurrence while continuous, normally distributed variables will be described by their mean and standard deviation; and continuous, non-normally distributed variables will be described by their median and range. The paired or unpaired Wilcoxon tests will be used to quantify differences in numerical outcomes while the Fisher's exact test and the McNemar's or Bowker's tests will be used to quantify changes in categorical variables.

If missingness occurs at random a mixed model will be utilized to assess the change in the lesion over time. A sensitivity analysis will be performed using the last observation carried forward and the results will be compared to that of the mixed-model.

Effect sizes will be estimated for the appropriate statistical tests that will be used for group comparisons in future studies. This will enable more accurate power and sample size estimates moving forward.

Bioinformatic Analysis:

RNA-seq analysis: We will use our recently developed LinNorm program (<https://www.bioconductor.org/packages/release/bioc/html/Linnorm.html>) to process RNA-seq data and detect differentially expressed genes (DEGs) by comparing the RNA-seq profiles. We will first find DEG between responsive and non-responsive samples from the same individual by using paired or unpaired Wilcoxon rank-sum test (depending on how the samples are collected). We will then rank each gene in the DEGs based on the occurrence frequencies in all 12 subjects

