to find common DEGs for responsiveness (use permutation test to determine the p value). For the top ranked genes (common DEGs), we will use DAVID (3) and GSEA (4) software to find enriched inflammatory pathways and GO terms for the DEGs. By comparing the normal tissue with the pathogenic tissue (responsive + non-responsive) using the above approach, we will detect a common DEGs for LP pathogenesis. Hierarchical clustering (5) and Principal Component Analysis (PCA) (6) will be applied to samples for their hierarchical relationship and clustering properties. Ideally normal, responsive and non-responsive tissues should form three distinct groups. The PCA analysis will provide us a set of gene signatures that can distinguish these three types of tissues. The common DEGs for responsiveness and pathogenesis, as well as gene signature from PCA will be used for our pathogenesis or survival prediction. We will perform structure variants calling from RNA-seq data with SNPiR (7), and reconstruct gene co-expression networks with ARACHNE.(8) Additionally, we will perform de-convolutional analysis, to compare the immune profiles of responsive and non-responsive tissue and to correlate immune profiles. Predictive biomarkers will be correlated with lesional and global responses.

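### Prediction of response is promised, but the only responsiveness contrast specified uses week-4 tissue already sorted by response, and no week-0 predictive analysis is defined

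*Combined protocol and SAP*

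**What the plan says.** **Aim.** The Study Summary gives one aim as "To predict responses through the identification of unique biomarkers of LP at week 0", together with RNA sequencing at week 4. Section 3 (Exploratory Objectives), repeated in Section 4.1, couples prediction of response with the pharmacodynamics of treatment. The means are "identification of unique biomarkers and transcriptomic changes of LP at week 0 and utilizing RNA sequencing on responsive and non-responsive tissue at week 4". Section 3 adds: "To correlate these biomarkers with measures of global response: Modified CAILS, PGA, BSA, and lesion count". Section 8.1 supports the small single-arm design partly with the statement "This will reduce costs and provide biomarkers predictive of response".

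**Samples.** Section 4.1 provides that at week 0 "up to two 3mm tissue biopsies will be taken from lesional skin and one biopsy will be taken from normal appearing skin". At week 4, up to two more biopsies come from responsive and refractory lesions. On the labels it says: "Responsive and non-responsive lesions will be determined by the change in Modified CAILS between week 0 and 4". Responsive means a 50% reduction in the score.

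**Analysis.** Section 8.2 begins: "We will first find DEG between responsive and non-responsive samples from the same individual". Genes are then ranked by how often they recur across the 12 subjects. A second contrast sets normal tissue against responsive and non-responsive tissue combined. Clustering and PCA look for the same three groups, and the deconvolution again compares responsive with non-responsive tissue. The results are put to this use: "The common DEGs for responsiveness and pathogenesis, as well as gene signature from PCA will be used for our pathogenesis or survival prediction". The section closes with one sentence saying that predictive biomarkers will be correlated with lesional and global responses.

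**The concern.** A predictive marker must be measured before treatment and related to what happens afterwards. The responsiveness contrast in Section 8.2 takes tissue after four weeks of cream and groups it by what has already happened. A gene that merely follows current inflammation will tend to differ between those groups, whether or not it differed at baseline.

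If Section 8.2 is followed as written, such genes could be carried forward as predictive markers. They would have no demonstrated use in an untreated patient. The prediction half of the objective would also have no defined analysis, although pre-treatment lesional tissue is collected and sequenced.

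**Working it through.** **1. Sample count (Section 4.1).** 12 subjects × (2 lesional + 1 normal at week 0 + 2 at week 4) = 60, which is the plan's own figure. By type:
- week-0 lesional: 12 × 2 = 24 (24/60 = 40%)
- week-0 normal: 12 × 1 = 12
- week-4 lesional: 12 × 2 = 24

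The lesional counts are maxima, since both are given as up to two per subject.

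**2. Which samples enter which analysis.**

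| Analysis | Tissue | Bears on prediction of response? |
|---|---|---|
| Responsive vs non-responsive genes (8.2) | Week-4 lesional | No: label and tissue are both post-treatment |
| Normal vs responsive + non-responsive (8.2) | Normal and week-4 lesional | No: addresses disease |
| Clustering, PCA, deconvolution (8.2) | Same groups | No |
| Treated vs untreated lesions (4.1) | Not stated; could include week-0 tissue | No: addresses drug effect |
| Correlation of biomarkers with response (3, 8.2) | Not stated | Possibly: no time point, tissue, test or unit given |

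No contrast in 8.2 names the week-0 lesional samples. No rule ties a week-0 biopsy to the later response of that lesion or subject.

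**3. Circularity.** The responsiveness genes are selected by a lesion-level label, so correlating them with lesional response reuses the selecting variable. PGA, BSA and lesion count are subject-level measures and not that label, so the charge applies less to them. The Appendix builds Modified CAILS from erythema, scaling, elevation and size. A 50% fall in this composite does not require each sign to halve.

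**4. Illustration of confounding by current severity.** All inputs here are assumptions, apart from the 12 subjects and the 50% cut-off. Responsive lesions sit at 0–50% of baseline score and non-responsive at 50–110%. Expression = ρ × standardised severity + √(1−ρ²) × noise, with no baseline predictive value. The test is a paired Wilcoxon across subjects at p<0.05, with 4,000 trials per case.

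| Complete pairs | ρ = 0.3 | ρ = 0.5 | ρ = 0.7 |
|---|---|---|---|
| 12 | about 20% | about 53% | about 90% |
| 8 | 12% | 31% | 66% |
| 6 | 8% | 18% | 39% |

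A week-0 test of the same gene against response is flagged in about 5%, the nominal rate, by construction.

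**5. What a week-0 analysis could show with 12 subjects.** Two-sided 0.05 is assumed, because the plan states no alpha.
- One prespecified marker, 80% power, Fisher z: r = tanh[(1.960 + 0.842)/√(n−3)]. For n = 12: tanh(2.802/3) = 0.73. For n = 10: 0.79. For n = 8: 0.85.
- Subjects split into responders and non-responders, smallest exact rank-sum p = 2/C(12,k). For 6 vs 6: 2/924 = 0.0022. For 4 vs 8: 2/495 = 0.0040. For 2 vs 10: 2/66 = 0.030.
- Bonferroni threshold with an assumed 10,000 genes: 0.05/10,000 = 5×10⁻⁶. With 20,000: 2.5×10⁻⁶. No gene could reach either by the rank-sum route. A continuous response measure removes that floor, but the observed correlation would then have to exceed about 0.9.

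**The case against.** **The link to response is promised.** Section 3 counts week-0 biomarkers among those to be correlated with Modified CAILS, PGA, BSA and lesion count, and 8.2 ends with a similar sentence. This stands. A reader might infer that week-0 tissue is never to be related to outcome, and the documents do not support that. They promise a link without specifying it, and the only responsiveness biomarkers that 8.2 generates come from week-4 tissue.

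**Week-4 tissue has a legitimate purpose.** Pharmacodynamics is part of the same objective, and the responsive-versus-refractory contrast suits it. This also stands. The fault lies in the use made of the result, not in taking the biopsies.

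**The contrast may include baseline differences.** It may. A reader might infer that it finds only consequences of healing. The documents do not show that; they show only that the sources cannot be separated.

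**The simulation follows from its assumptions.** True: the gene is defined to follow severity and the two severity ranges do not overlap. The simulated test is also simpler than the plan's recurrence ranking with a permutation test. Twelve complete pairs is the best case, since week-4 sampling is up to two biopsies and Section 5.1 admits subjects with 4 lesions. The figures show a mechanism; they do not estimate this trial's error rate.

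**The study is small and exploratory.** Section 8.2 says it is for estimation only. That limits what a week-0 analysis can deliver and how serious the gap is, but it does not make post-treatment genes predictive.

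**Conclusion.** The point holds in this form. Prediction of response is a stated objective and part of the case for the design, yet the only specified route to responsiveness genes uses week-4 tissue classified by the outcome. Those genes and the PCA signature should not be called predictive, and correlating them with lesional response is circular. Up to 24 of 60 samples are week-0 lesional tissue with no named contrast in 8.2. Survival prediction matches none of the endpoints in Sections 4.4 and 4.5.

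This conclusion rests on the text and not on the simulation. It assumes that the responsive and non-responsive labels in 8.2 carry the week-4 meaning given in Sections 3 and 4.1; no other meaning is offered.

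A reader might also infer that the collected samples are enough to answer the prediction question. They are not: with 12 subjects, a single marker needs a correlation of about 0.73 for 80% power. No primary or secondary endpoint is affected. This is a cheap improvement to an exploratory objective.

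**What to change.** In Section 8.2:

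1. **Define the predictive analysis.** Relate week-0 lesional expression, relative to the same subject's week-0 normal skin, to later response with the subject as the unit, at week 4 and again at week 8.
2. **Define response for it.** Use (a) the change in Modified CAILS of the treated index lesion and (b) the proportion of treated, non-index, non-biopsied lesions with at least a 50% reduction. State which lesions are biopsied, because the plan does not say, and a 3 mm biopsy of a lesion that may be only 5 mm wide could alter its later score. Note that (b) is coarse: a subject with 4 lesions has at most 4 − 2 = 2 non-index lesions, and none is left if both are biopsied.
3. **Select predictive candidates only from this analysis.** Use a short prespecified list of genes or pathways, name the test and the multiplicity rule, and report estimates with intervals as hypothesis-generating.
4. **Keep the week-4 contrast, PCA and deconvolution, labelled pharmacodynamic.** Do not describe their output as predictive.
5. **Delete the reference to survival prediction**, and soften the sentence in Section 8.1 to match.

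Cost: wording changes and a little more analysis on samples already planned for sequencing, with no extra visits or biopsies. The downside is a more modest prediction claim.

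### Lesional biomarker correlations are computed in the 12 subjects whose lesion responses selected the genes, so under most readings of 8.2 they are biased upward and cannot support a claim of prediction

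*Combined protocol and SAP*

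**What the plan says.** Section 4.1 takes up to two biopsies per subject at week 4: "At week 4, up to two 3mm biopsies will be taken from lesional responsive tissue and lesional refractory tissue". The label comes from the lesion score: "Responsive will require a 50% reduction in Modified CAILS and non-responsive can have progression, no change, or up to a 50% reduction in Modified CAILS".

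Section 8.2 (Bioinformatic Analysis) uses that label to select genes: "We will first find DEG between responsive and non-responsive samples from the same individual". Genes are then ranked by how often they appear as differentially expressed genes (DEGs) across all 12 subjects, and a permutation test gives a p value for the common ones. The selected genes are put to use: "The common DEGs for responsiveness and pathogenesis, as well as gene signature from PCA will be used for our pathogenesis or survival prediction". The closing step is "Predictive biomarkers will be correlated with lesional and global responses".

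The exploratory objective in section 3 is "To correlate these biomarkers with measures of global response: Modified CAILS, PGA, BSA, and lesion count". Section 8.1 justifies a 12-subject single-arm study partly because it will yield markers that predict response. Section 8.2 also says: "With 12 subjects, the study is intended to be for estimation purposes only".

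No second cohort, hold-out set, cross-validation or false-discovery rule is given. The permutation unit, and whether the test covers all genes, are not stated.

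**The concern.** The label that picks the genes is a cut of the variable with which they are later correlated. A gene enters the list because, in these lesions, it happens to differ between those with large and small falls in Modified CAILS. Correlating it with lesional response in the same lesions partly restates the selection. Chance differences among thousands of genes then appear as association, and nothing planned separates them from a real marker.

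At stake is the exploratory objective and part of the case for the design. A high in-sample correlation could be reported as a predictive marker, or used to plan a later study, although it would be expected with no true marker at all.

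**Working it through.** **Inputs from the documents.** 12 subjects (8.2). Up to three biopsies at week 0 and two at week 4 (4.1): 12 × (3 + 2) = 60, which reproduces the stated sample count. Two week 4 biopsies per subject give at most 12 responsive/non-responsive pairs, or 24 lesions. The plan states no figure for the correlation itself.

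**Assumptions.** The documents give no gene count, signature size or direction rule. The main simulation uses 15,000 independent genes, none related to response; subject and residual SD of 1 (within-subject correlation 1/(1 + 1) = 0.5); reductions uniform on 50 to 95% in responsive lesions and −10 to 49% in non-responsive lesions; 60 replicates. With one biopsy of each kind, a Wilcoxon test inside one subject has no replication, so the test is read as running across the 12 pairs.

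**Step 1: null genes that separate the labels perfectly.** The smallest two-sided paired Wilcoxon p with 12 pairs is 2/2^12 = 0.00049. Expected number of null genes with all 12 differences in one direction: 15,000 × 0.00049 = 7.3. If only 8 subjects supply both lesion types, the figures are 2/2^8 = 0.0078 and 15,000 × 0.0078 = 117.

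**Step 2: signature against lesional response, 24 lesions.** The signature is the mean of the selected genes, each given the sign it shows in the same data.

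| Selection rule | In-sample mean r | Selection repeated, one subject left out |
|---|---|---|
| Top 50 by paired t | 0.83 | −0.05 to −0.01 |
| Top 50 by occurrence frequency, same direction | about 0.8 | about 0 |
| Top 50 by occurrence frequency, either direction | about 0.65 | about 0 |
| All genes with unadjusted p < 0.05 | 0.87 | 0.00 |

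The last row carries forward about 15,000 × 0.05 = 750 null genes.

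**Step 3: single genes, no signature.** This used 5,000 or 20,000 null genes, within-subject correlation 0 or 0.5, and the top 20 genes.
- Paired Wilcoxon selection: mean |r| across 24 lesions is 0.34–0.50, against 0.14–0.17 for unselected genes. Within pairs it is 0.71–0.75 against 0.235. In new data the selected genes return to 0.13–0.17 and 0.23–0.24.
- Occurrence frequency, same direction: 0.23–0.30 across lesions and 0.36–0.39 within pairs.
- Occurrence frequency, either direction: 0.16–0.19 across lesions and 0.23–0.24 within pairs, so essentially no inflation.

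**Step 4: the permutation test.** A maximum-statistic sign-flip test over 20,000 genes let a null gene through in 4% of 100 null runs. A per-gene test at 0.05 would pass about 5% of null genes, as in the last row of the table.

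**Step 5: subject-level global response.** Genes selected on the within-subject contrast have mean |r| 0.24–0.25 with an unrelated subject-level outcome at n = 12, against 0.246 without selection. About 5% reach p < 0.05, as expected by chance. Selection adds nothing here. Testing many genes does: for 20 independent genes, 1 − 0.95^20 = 0.64 is the chance that at least one reaches p < 0.05, and the best of 20 averages |r| about 0.60–0.63. This is for one measure; section 3 lists four.

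**The case against.** The strongest reply is that 8.2 does not fix the pipeline simulated here. It gives no top-50 cut and no averaging, and it does not say that occurrences must agree in direction. If they need not agree and genes are never oriented by the data, the lesional inflation largely vanishes. The permutation test supplies the list of common DEGs; if it controls error over all genes, few null studies would carry any gene forward. The biomarkers to be correlated are not defined: section 3 also names week 0 markers, and 8.2 lists principal-component signatures and immune deconvolution, none of which need be week 4 DEGs. The work is exploratory, in a pilot meant for estimation.

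Much of this stands. It rules out saying that a strong correlation is guaranteed, or that the objective would appear met whatever the truth. It does not remove the problem. The protective readings are not written down, and orienting genes in the same data restores the inflation even when frequency ignores direction. No separate selection or validation rule is given for the other markers. The exploratory label does not cover the claim in 8.1 that markers will predict response.

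A reader might extend the circularity to all global responses. Step 5 does not support that for PGA, BSA or lesion count. Modified CAILS is also listed as a global measure, and there overlap with the selection label is possible. A reader might also note that the best of 15,000 null genes screened directly against a subject-level response reaches |r| of about 0.91 at n = 12. Section 8.2 describes no such screen, so that figure does not measure this plan.

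**Conclusion.** The point holds for lesional response. Selection and correlation use the same 12 subjects and a label derived from the same score, with no validation that repeats the selection. Under most readings the reported lesional correlation is biased upward: about 0.65 to 0.83 for an oriented 50-gene signature when no gene matters, against about 0 when selection is repeated with each subject left out. These sizes rest on the assumed gene count, independence, signature size and orientation rule. Correlated genes would change the figures but not the direction. A permutation test controlling error over all genes would reduce the bias, but the plan does not say that it does.

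For PGA, BSA and lesion count the defect is uncontrolled multiplicity across genes and measures, not selection bias.

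Separately, 8.2 speaks of predicting survival, while 4.4 and 4.5 define no survival endpoint. A reader might infer that no survival information is collected at all. That is too strong: 9.3.1 refers to a death and survival form and 10.1 to vital status.

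**What to change.** Add a paragraph to 8.2 along these lines:

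- Correlations with, or predictions of, lesional response are called predictive only when computed leaving one subject out, with normalisation, DEG selection, ranking, gene orientation and signature building repeated in each fold.
- P values come from permuting response labels through the whole pipeline, with error control over all genes tested. State the permutation unit. For global responses, control also covers the measures tested.
- In-sample correlations are labelled descriptive and hypothesis-generating.
- The reference to predicting survival is replaced by response prediction.

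State also which markers enter the correlation step (week 4 DEGs, week 0 markers, principal-component signatures, immune profiles) and whether occurrences must agree in direction.

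The cost is computing time and one paragraph, with no new subjects, visits or samples. The reported correlations will be less favourable, and leave-one-out estimates from 12 subjects will be variable. If the sponsor prefers not to run the nested analysis, the results can still be reported as hypothesis-generating, but 8.1 should then drop its claim that the study provides markers that predict response.
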